14.3 Primary and Secondary End Point Analyses

14.3.1 Primary End Point Analysis: The primary objective will be to compare the effects of supervised linear aerobic training (Arm A) versus supervised nonlinear aerobic training (Arm B), relative to progressive stretching (attention-control group) (Arm C), on VO_{2peak} in women with operable breast cancer following the completion of primary adjuvant therapy.

An intent-to-treat statistical analysis will be conducted. Baseline characteristics will be compared using the Fisher exact test for categorical variables or a Wilcoxon rank sum test for continuous variables. The primary end point comparison will be analyzed using a multiple regression model to test for differences among and between the study arms in VO_{2peak} from baseline to the follow-up assessment (Week 17). The regression model will include the stratification factors [i.e., treatment with chemotherapy (yes vs. no) and current treatment with endocrine therapy (yes vs. no)].

In the absence of evidence to the contrary, multiple imputation strategies for missing Week 17 VO_{2peak} data will be performed assuming data were missing at random using logistic regression. Results will be aggregated over 20 imputed sets using the variance formula by Rubin. In addition, a per-protocol analysis will be performed using a multiple regression model to test for differences among and between the study arms in VO_{2peak} from baseline to the follow-up assessment (Week 17) on the basis of exercise adherence to the supervised aerobic training sessions (<80% versus ≥80%). In the event that groups are unbalanced on medical or demographic characteristics at baseline, we will also perform a sensitivity analysis that includes these factors in the model.

14.3.2 Secondary End Point Analyses: As for the primary end point, the intention-to-treat principle will be employed for analysis of all secondary end points. Multiple regression models will be used to test for differences among and between the study arms in secondary end points from baseline to the follow-up assessment (Week 17). The regression model will include the baseline value of the end point, as well as any other baseline characteristics that are not balanced between groups. All secondary end points are continuous.

In the absence of evidence to the contrary, multiple imputation strategies for missing Week 17 end point data will be performed assuming data were missing at random using logistic regression, as described above. Again, a per-protocol analysis will be performed using a multiple regression model to test for differences among and between the study arms in secondary end points from baseline to the follow-up assessment (Week 17) on the basis of exercise adherence to the supervised aerobic training sessions (<80% versus ≥80%). Finally, we will also perform a sensitivity analysis in the event that groups are unbalanced on medical or demographic characteristics at baseline.

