14.1 BIOSTATISTICS

14.2 Sample Size Calculation and Justification

The power of both an overall F-test comparison for the study's primary outcome variable, exercise capacity (VO_{2peak}), among study arms is considered as part of power calculations, as well as two primary pairwise comparisons (i.e., Arm A versus Arm B; Arm B versus Arm C). The power of pairwise comparisons is computed with adjustment for multiple comparisons using a Bonferroni correction factor ($\alpha=0.05/2 = 0.025$). The comparison of Arm A vs. Arm C is also of interest but is not a primary pairwise comparison.

The power estimates were calculated using the following observed/expected change in VO_{2peak} from baseline to Week 17:

- Arm A: $+1.5 \text{ mL.kg}^{-1}\text{min}^{-1}$
- Arm B: $+4.0 \text{ mL.kg}^{-1}\text{min}^{-1}$
- Arm C: $0.0 \text{ mL.kg}^{-1}\text{min}^{-1}$

Power estimates assume the SD for the change in VO_{2peak} to be equal for all these groups ($4.0 \text{ mL.kg}^{-1}\text{min}^{-1}$) obtained from our prior work among post therapy breast cancer patients.^{11,12} In accordance to the principles of intention-to-treat, 174 patients will have evaluable post-intervention follow-up providing >99% power to detect the noted difference among the three experimental groups with an F-test conducted with two degree of freedom. With 58 patients per group having evaluable post-intervention follow-up, there is 86% power to detect a $2.5 \text{ mL.kg}^{-1}\text{min}^{-1}$ difference in VO_{2peak} between Arms A and B; and >99% power to detect a $4.0 \text{ mL.kg}^{-1}\text{min}^{-1}$ difference in VO_{2peak} between Arm B and Arm C using a two-sided alpha of 0.025.

A final important consideration when conducting exercise RCTs is extent of exercise "drop-in" or contamination in Arm C. In other words, the concern is that patients assigned to attention-control may independently initiate an exercise training program which, in turn, potentially dilutes the efficacy of aerobic training on the outcomes of interest. However, we feel this is less of a concern in the present study because patients in the aerobic training arms (Arm A and B) will be provided with a personalized exercise prescription. which will be difficult to replicate without sophisticated prescription algorithms and expertise. In addition, attention control participants are also provided with a supervised attention intervention.

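### Free improvement: the primary VO2peak regression does not name baseline VO2peak as a covariate, although every secondary model names its baseline value

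*Combined protocol and SAP*

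**What the plan says.** Section 14.3.1 describes the primary analysis as a multiple regression "to test for differences among and between the study arms in VO_{2peak} from baseline to the follow-up assessment (Week 17"). The only covariates it names are in this sentence: "The regression model will include the stratification factors [i.e., treatment with chemotherapy (yes vs. no) and current treatment with endocrine therapy (yes vs. no").

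Section 14.3.2 describes the secondary analyses in the same terms, as differences between arms from baseline to Week 17, but then adds: "The regression model will include the baseline value of the end point, as well as any other baseline characteristics that are not balanced between groups".

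The only provision in section 14.3.1 for imbalance is conditional: "In the event that groups are unbalanced on medical or demographic characteristics at baseline, we will also perform a sensitivity analysis". It does not mention VO2peak. Randomization (section 15.3) is stratified on chemotherapy and endocrine therapy, not on baseline VO2peak.

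Section 14.2 names "two primary pairwise comparisons (i.e., Arm A versus Arm B; Arm B versus Arm C") and tests each "using a two-sided alpha of 0.025". Its power figures use the SD of the change in VO2peak, with no allowance for baseline adjustment. Section 12.1 has every potential participant perform two baseline exercise tests and uses the second in the analyses if both are acceptable.

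**The concern.** Baseline VO2peak is measured before randomization, and an acceptable baseline test is an eligibility requirement. It is likely to be one of the strongest available predictors of Week 17 VO2peak. As written, the secondary end points get this adjustment and the primary end point does not, and no reason is given.

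Two things follow for a change score analysed without the baseline covariate. First, the residual variance is larger than it needs to be. Second, an arm that by chance starts low will tend to show a larger gain through regression to the mean, and the model does not remove this. Arm A versus Arm B is where it matters most: its stated power is 86%, whereas B versus C and the overall F-test are both above 99%.

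**Working it through.** **Inputs from section 14.2.** Expected changes are +1.5 (A), +4.0 (B) and 0.0 (C) mL/kg/min, so the A-versus-B difference is 4.0 − 1.5 = 2.5. The SD of change is 4.0 in each arm, with 58 evaluable patients per arm and two-sided alpha 0.05/2 = 0.025.

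**Assumptions, not in the documents.** Rho is taken over the range 0.5 to 0.9, with equal variances at baseline and Week 17.

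**Step 1: reproduce the plan's figure.** The standard error of the A-versus-B difference in change is 4.0 × √(2/58) = 0.743. The noncentrality is 2.5/0.743 = 3.37. On 114 degrees of freedom the critical t is 2.27, and power is 0.8615. This agrees with the stated 86%, so that figure is for a change score without baseline adjustment.

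**Step 2: add the baseline covariate.** With common variance σ², the change score has variance 2σ²(1 − rho) and the baseline-adjusted outcome has residual variance σ²(1 − rho²). Their ratio is (1 + rho)/2, so the residual SD becomes 4.0 × √((1 + rho)/2). Power uses the same noncentral t on 114 degrees of freedom.

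| rho | Variance reduction | Residual SD | A-versus-B power |
|---|---|---|---|
| none (unadjusted) | – | 4.00 | 86% |
| 0.5 | 25% | 3.46 | 94.5% |
| 0.6 | 20% | 3.58 | 93.1% |
| 0.7 | 15% | 3.69 | 91.4% |
| 0.8 | 10% | 3.79 | 89.7% |
| 0.9 | 5% | 3.90 | 88.0% |

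Using the pooled three-arm error (168 degrees of freedom) changes these powers by no more than about 0.2 points. A simulation of 3,000 trials gave 95.2% adjusted against 86.9% unadjusted at rho 0.5, and 89.9% against 86.2% at rho 0.8.

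**Step 3: exposure to chance imbalance.** The change score already subtracts the whole baseline difference; the correct amount is rho times that difference, so (1 − rho) of it remains in the contrast with the sign reversed. Holding the SD of change at 4.0 implies a baseline SD of σ = 4.0/√(2(1 − rho)). One standard error of baseline difference is then σ√(2/58).

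| rho | Implied baseline SD | 1-SE imbalance | Shift in contrast, (1 − rho) × imbalance |
|---|---|---|---|
| 0.5 | 4.00 | 0.74 | 0.37 |
| 0.7 | 5.16 | 0.96 | 0.29 |
| 0.8 | 6.32 | 1.17 | 0.23 |
| 0.9 | 8.94 | 1.66 | 0.17 |

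Units are mL/kg/min, against a target difference of 2.5. A two-standard-error imbalance doubles the shift.

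**The case against.** The best defence is that nothing here is an error. Under randomization the unadjusted change-score contrast is unbiased, and omitting the covariate does not inflate its type I error. The sample size took no credit for baseline adjustment, so the plan delivers the power it promises. A reader might infer that the trial is underpowered or its primary result biased; the documents do not support that, because the 86% reproduces without the covariate. This part of the defence stands.

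The size of the gain also depends on a correlation that the documents do not give. At rho 0.8 to 0.9 it is only about 2 to 4 power points. Fixing the SD of change at 4.0 while rho varies implies baseline SDs from 4.0 to 8.9, and no baseline SD is given to narrow that range. This stands too, and is why only a range can be reported.

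Section 14.3.1 does not say its covariate list is complete. Section 14.3.2 has the mirror gap: it names the baseline value but not the stratification factors. So a reader who inferred a deliberate exclusion of baseline VO2peak would be going beyond the text; compressed drafting is a fair explanation. It does not close the gap, since a primary model should not need guessing.

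A reader might also infer that the outcome is the raw Week 17 value with no baseline term. At the same SD of change, power would then be about 63% (rho 0.7), 45% (0.8) or 23% (0.9). The outcome form is never stated outright, but the from-baseline wording and the SD of change in section 14.2 both point to a change score, so those figures do not describe the plan.

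Finally, stratifying on chemotherapy and the imbalance sensitivity analysis offer some protection. It is partial: the sensitivity analysis is triggered by observed imbalance, is not primary and does not name VO2peak.

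**Conclusion.** The point holds as a free improvement, not as a flaw that invalidates the primary analysis. Section 14.3.1 does not name baseline VO2peak, section 14.3.2 does name the baseline value, and no other section supplies it for the primary model.

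Adjustment would cut the residual variance by between 5% (rho 0.9) and 25% (rho 0.5), worth roughly 2 to 8 points of A-versus-B power. It would also remove a shift of about 0.17 to 0.37 mL/kg/min per standard error of chance imbalance.

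These sizes rest on the assumed rho, on equal variances at the two times and on the plan's own SD and evaluable numbers. The direction does not depend on equal variances: the change score fixes the baseline slope at one while the adjusted model estimates it, so in large samples, with a common slope across arms, adjustment is never less efficient.

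**What to change.** In section 14.3.1, state that Week 17 VO2peak (equivalently, change from baseline) is regressed on arm, baseline VO2peak, prior chemotherapy and current endocrine therapy. With baseline in the model the two outcome forms give the same arm contrast, so this also settles the unstated outcome form. Define baseline VO2peak as the baseline test value selected by the section 12.1 rule, and have that section say which value is used when only one of the two tests is acceptable. Use the same covariates in the imputation and per-protocol models.

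No new data, patients or procedures are needed, and the model loses one degree of freedom. The administrative cost is more than a line of text. The trial is open-label, 115 of the 174 participants were randomized at the first site, and the statistical center there holds their data. The change should therefore be a documented amendment, routed through both institutional review boards where section 16.2 (Role of Duke University Medical Center) requires it, with a statement that it was made without knowledge of outcomes by arm.

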9.6 Study Intervention Continuation/Interruption

If a session is missed or interrupted for an adverse event (AE), the participant will be treated for the AE as per the discretion of the attending oncologist and/or PI, as appropriate. The participant will resume the intervention only after clearance from the PI.

Participants with treatment interruptions lasting longer than 4 consecutive weeks will be discontinued from the trial. In addition, any participant who misses a cumulative total of 8 weeks of the study intervention will be discontinued from trial participation. When appropriate, study follow-up assessments will still be performed.

When intervention sessions are resumed, the dosing will be progressively increased until the planned prescription can be safely resumed, according to the Ex-Onc Exercise Physiology standards of care and/or at the discretion of the Program Director.

Participants will be allowed to make up missed sessions within the 16-week study window. Participants are not allowed to *a priori* bank aerobic training sessions.

Participants experiencing disease recurrence will be removed from study.

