15.3 Randomization

Participants will be randomly allocated, on an individual basis, to one of the three study groups.

Randomly allocated participants will remain in the same group for the entire duration of the intervention (i.e., no cross-over). To ensure randomized groups are similar at baseline, patient randomization will be stratified based on prior treatment with chemotherapy (yes vs. no) and current treatment with endocrine therapy (yes vs. no). Chemotherapy causes greater reductions in VO_{2peak} relative to other types of cancer therapy (e.g., radiotherapy); thus, it is important for groups to be balanced on this factor. Similarly, current treatment with endocrine therapy is also expected to influence the effect of aerobic training on VO_{2peak} and other endpoints; thus it is important to ensure that groups are also balanced on this variable.

A permuted block design with allocation weight of 1:1:1 is used to generate the treatment assignments. Following the successful completion of all baseline assessments, Ex-Onc staff will enter randomization criteria into REDCap. Upon confirmation of stratification factors (chemotherapy treatment and/or endocrine treatment), REDCap will electronically randomize the patient.

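### Missing Week 17 VO2peak is imputed under missing at random only, with an undefined exception and no planned analysis that departs from that assumption

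*Combined protocol and SAP*

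**What the plan says.** Section 14.3.1 describes the primary analysis as intent-to-treat. Its missing-data sentence begins "In the absence of evidence to the contrary, multiple imputation strategies for missing Week 17" and goes on to assume MAR, name logistic regression as the method, and combine 20 imputed sets with Rubin's variance. Section 14.3.2 repeats this for the secondary end points: "multiple imputation strategies for missing Week 17 end point data will be performed assuming data were missing at random". Neither section lists the variables in the imputation model.

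Two further analyses are planned: a per-protocol analysis by adherence (below 80% versus 80% or more), and a sensitivity analysis that adds baseline characteristics found to be unbalanced. Neither changes the missing-data assumption.

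On who might lack a Week 17 value, section 9.6 states "Participants with treatment interruptions lasting longer than 4 consecutive weeks will be discontinued from the trial", applies the same consequence to a cumulative 8 missed weeks, and removes women with recurrence from the study. The same section still provides for follow-up assessments where suitable. Table 3 in section 13.0 asks for the required follow-up assessments after a woman stops the intervention, unless she declines them.

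Section 14.2 makes no allowance for loss: it assumes that "174 patients will have evaluable post-intervention follow-up".

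**The concern.** Observed outcomes cannot by themselves show whether data are missing at random. An exception that depends on contrary evidence therefore needs a stated trigger, such as a pattern in reasons for stopping or unequal loss by arm, and a stated alternative. The plan has neither, so in practice MAR is the only analysis, or a departure from it would be chosen after the data are seen.

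Here MAR is worth testing. The rules in section 9.6 and Table 3 tie leaving the trial to interrupted training, adverse events, non-compliance, withdrawal and recurrence, so a missing Week 17 test is plausibly related to training exposure. If the imputation uses arm but not attendance, a woman who left Arm B without a Week 17 test receives values centred on the observed Arm B mean. If women like her gained less than that, the effects of B over C and of B over A are overstated. B versus A is the more exposed of the two primary comparisons because its assumed difference is smaller. Arm B trains at up to 100% of VO2peak and Arm A at up to 75% (sections 9.3.1 and 9.3.2), so unequal loss is conceivable.

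**Working it through.** **Inputs.** From section 14.2:
- assumed changes of A +1.5, B +4.0 and C 0.0 mL/kg/min;
- "Power estimates assume the SD for the change in VO_{2peak} to be equal for all these groups", at 4.0;
- 58 evaluable women per arm, and each primary pair tested "using a two-sided alpha of 0.025".

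Loss at the first site is 6 of 115 (5.2%) in section 1.0 and 9 of 115 (7.8%) in section 16.3. The two figures conflict, so both are used as a range.

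**Step 1: reproduce the plan's power.** The plan says "With 58 patients per group having evaluable post-intervention follow-up, there is 86% power to detect a" difference of 2.5.
- Standard error of a pairwise difference = 4 × √(2/58) = 0.743.
- Noncentrality = 2.5 / 0.743 = 3.37. With 114 degrees of freedom and two-sided 0.025, noncentral t power is 86.2%. The stated 86% reproduces.
- B versus C, difference 4.0: 99.9%, consistent with the stated figure of over 99%.

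**Step 2: bounding assumption.** Take the plan's gains as the means among women with a Week 17 test, and suppose that women without one gained nothing, which is Arm C's assumed change. Arm-based MAR imputation without attendance then still aims at 2.5 and 4.0. With missing fractions fA and fB, the effect over all randomized women is:
- B minus A = 4.0(1 − fB) − 1.5(1 − fA)
- B minus C = 4.0(1 − fB)

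**Step 3: documented loss rates, balanced across arms.** Power here is for the reduced difference at 58 per arm with SD 4.0.

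| Loss per arm | B minus A | Overstatement | In standard errors | Power, B vs A | B minus C | Power, B vs C |
|---|---|---|---|---|---|---|
| 0 | 2.50 | 0 | 0 | 86% | 4.00 | 99.9% |
| 5.2% | 2.37 | 0.13 | 0.18 | 82% | 3.79 | 99.7% |
| 7.8% | 2.30 | 0.20 | 0.26 | 80% | 3.69 | 99.6% |

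If missing women kept half the gain, the overstatement of B minus A halves, to 0.07 and 0.10.

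**Step 4: unequal loss (assumed, not documented).** With 5% missing in A and 15% in B:
- Zero gain kept: 4.0 × 0.85 − 1.5 × 0.95 = 3.400 − 1.425 = 1.975. MAR overstates by 0.525, and power for 1.975 is 65%.
- Half the gain kept: 4.0 × 0.925 − 1.5 × 0.975 = 3.7000 − 1.4625 = 2.24, with power 77%.

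**Step 5: outer bound (assumed).** Scale the first site's loss to 174 women and place all of it in Arm B.
- 6/115 × 174 = 9.1 women, 15.7% of 58: B minus A = 4.0 × 0.843 − 1.5 = 1.87.
- 9/115 × 174 = 13.6 women, 23.5% of 58: B minus A = 4.0 × 0.765 − 1.5 = 1.56.

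The overstatement is then 0.63 to 0.94. For scale, a difference must exceed about 2.271 × 0.743 = 1.69 to be significant at 0.025. Only the last case falls below that.

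**The case against.** The strongest reply is that the plan limits the problem. Sections 9.6 and 13.0 intend Week 17 testing for many women who stop. Their observed values enter the analysis as they are, and only women who have no test are imputed. That stands, and it confines the point to those women. It does not remove the point: follow-up under section 9.6 is discretionary, women may decline it, and recurrence means removal.

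A reader might infer that every woman who stopped training is credited with the full gain of women who trained. The documents do not support that. The imputation covariates are unstated, which is not the same as attendance being excluded. The observed women who would inform the imputation include partly adherent ones: mean adherence in Arms A and B was 77% (section 16.3). First-site losses are recorded only as lost to follow-up, with no reason or training status.

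A reader might also infer that the exception could never apply. Recorded reasons for stopping, attendance or unequal loss could be offered as evidence against MAR. The defect is that no trigger or alternative is defined.

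Finally, the size is small at documented loss if loss is balanced: at most about a quarter of a standard error for B minus A, with B versus C power still above 99%. That also stands.

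**Conclusion.** The point holds in limited form. MAR is the sole missing-data assumption, the exception to it is not operational, the imputation model is unspecified, and no planned analysis departs from MAR.

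The possible overstatement of B minus A is 0.13 to 0.20 mL/kg/min at the documented loss rates. This rests on three assumptions: balanced loss, zero gain among women with no Week 17 test, and an imputation by arm that ignores attendance. The B versus C conclusion is not threatened on those terms. A large bias in B minus A, such as the 0.53 from a 5% and 15% split, should not be read as an estimate, because the documents give no loss by arm and the split is assumed. It shows only that the comparison is sensitive to where loss falls. The change is worth making before analysis, but the point does not undermine the design.

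**What to change.** In section 14.3.1:

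1. Delete the conditional clause that opens the missing-data sentence, and state MAR as the assumption of the primary analysis.
2. State the imputation model: arm, baseline VO2peak, the two stratification factors and sessions attended. Attendance is already collected under section 9.7. Name a method for a continuous outcome, since logistic regression does not suit VO2peak.
3. Add one prespecified sensitivity analysis, only for women with missing Week 17 VO2peak, that imputes those in Arms A and B from Arm C. Observed Week 17 values stay as they are, including those from women who stopped.
4. Report a delta tipping point for B versus A and for B versus C: how far the imputed values must be shifted before each comparison loses significance at 0.025.

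Two terms should not be required in the model. A within-arm indicator for discontinuation would be barely estimable with roughly 3 to 5 missing women per arm (58 × 5.2% = 3.0; 58 × 7.8% = 4.5). The Week 8 VO2peak exists only in Arm B (section 10.1) and would treat the compared arms asymmetrically.

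The cost is a short text change and a little programming, with no new data. The downside is a sensitivity estimate slightly less favourable to training.

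### Logistic regression is named as the imputation method for continuous end points, and the plan does not say how arm or baseline would enter it

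*Combined protocol and SAP*

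**What the plan says.** Section 14.3.1 sets the principle: "An intent-to-treat statistical analysis will be conducted". The primary comparison is a multiple regression on VO2peak from baseline to Week 17 with the two stratification factors as covariates, so the outcome is treated as continuous. For missing values, "multiple imputation strategies for missing Week 17 VO_{2peak} data will be performed assuming data were missing at random using logistic regression". Pooling follows: "Results will be aggregated over 20 imputed sets using the variance formula by Rubin".

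Section 14.3.2 carries the method over to the secondary end points, "performed assuming data were missing at random using logistic regression, as described above", and states of those end points: "All secondary end points are continuous".

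Neither section says what the logistic regression predicts, which variables are in it, whether arm or the baseline value is among them, or how an imputed value is generated.

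**The concern.** A logistic regression has a categorical response. It cannot produce a VO2peak value in mL/kg/min unless the outcome is first cut into categories, which would not feed the planned regression. The named method therefore does not fit the variable it is meant to impute, and the mismatch covers the primary end point and every secondary one.

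One workable reading exists. The logistic model predicts whether Week 17 is missing, participants are grouped by that predicted probability, and missing values are drawn from observed donors in the same group. This is a recognised form of multiple imputation for continuous data, but its result depends on details the plan omits. If donors come from all arms without regard to allocation, imputed participants resemble the average of the three arms and the arm contrasts shrink. If donors come from the participant's own arm, they do not. Two statisticians following the text could report different primary estimates. The trial is open label (Section 7.1, Blinding), so this choice is better not left until after the data are seen.

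**Working it through.** **Inputs.** Section 14.2: mean changes of 1.5 (Arm A), 4.0 (Arm B) and 0.0 (Arm C); SD of change 4.0; 58 evaluable per arm; two-sided alpha 0.025 per primary pairwise comparison; stated power 86% for A versus B and above 99% for B versus C. Loss at the first site: 6 of 115 (Section 1.0) or 9 of 115 (Section 16.3). The two counts disagree, so both are used as a range. The share with missing Week 17 VO2peak is assumed equal to the share lost.

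**Step 1: the plan's own figure.** The standard error of the A–B difference is 4.0 × √(2/58) = 0.743. The noncentrality is 2.5/0.743 = 3.37. With 114 degrees of freedom and two-sided alpha 0.025, the noncentral t gives 86.2%. For B versus C (4.0) it gives 99.9%. Both stated figures reproduce. They assume no missing data.

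**Step 2: how much is missing.** 6/115 = 5.2% and 9/115 = 7.8%. Applied to 174, that is 9.1 or 13.6 participants. The evaluable number per arm becomes 58 × (1 − 0.052) = 55.0 or 58 × (1 − 0.078) = 53.5. A complete-case comparison of the full 2.5 then has 84.1% or 82.9% power. This, not 86%, is the fair comparator for an imputation method.

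**Step 3: attenuation if arm is ignored.** Let a fraction *m* of each arm be replaced by draws from the pooled donors, whose mean is the average over arms. Each arm mean becomes (1 − *m*) × own mean + *m* × pooled mean. In a difference the pooled term cancels, leaving (1 − *m*) × true difference.

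- A–B: 2.5 × (1 − 6/115) = 2.37; 2.5 × (1 − 9/115) = 2.30.
- B–C: 4.0 × (1 − 6/115) = 3.79; 4.0 × (1 − 9/115) = 3.69.

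The A–B shift of 0.13 or 0.20 is 0.130/0.743 = 0.18 or 0.196/0.743 = 0.26 of a standard error.

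**Step 4: simulation of the readings.** 1,000 trials per loss rate, 58 per arm, the Section 14.2 means and SD, loss completely at random and equal across arms, 20 imputations, Rubin's rules. The propensity versions used five strata and an approximate Bayesian bootstrap, with covariates unrelated to the change.

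| Method | A–B at 5.2% | Power | A–B at 7.8% | Power |
|---|---|---|---|---|
| Complete cases | 2.48 | 83.6% | 2.49 | 83.3% |
| Linear regression with arm | 2.48 | 83.5% | 2.49 | 83.1% |
| Logistic missingness model, draws within arm | 2.48 | 83.6% | 2.49 | 83.1% |
| Logistic missingness model, arm as a predictor only | 2.39 | 81.7% | 2.35 | 79.6% |
| Logistic missingness model, arm left out | 2.36 | 80.1% | 2.30 | 77.1% |

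The "draws within arm" row takes each arm as a single donor group. Against linear imputation, leaving arm out costs 83.5 − 80.1 = 3.4 points or 83.1 − 77.1 = 6.0 points. Using arm only as a predictor in the missingness model costs 1.8 or 3.5. B–C power is at least 99.8% in every row. At an assumed 15% loss, the arm-omitted reading gives A–B 2.12 and power 65%, against 2.49 and 79% for linear imputation.

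**The case against.** The strongest reply is that the plan is runnable. Logistic regression of missingness is an established step in propensity-score imputation, and with donors drawn within arm it recovers 2.48–2.49. The text never says that donors are pooled across arms or that baseline is ignored. It also speaks of imputation strategies in the plural and makes the missing-at-random assumption conditional. Few values are affected (about 9 to 14 of 174), complete cases give the same answer when loss is completely at random, and the attenuation computed here is conservative.

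Most of this stands, and it rules out two stronger readings. A reader might infer that the primary estimate cannot be computed, or that it must be pulled toward zero; the documents support neither, because they leave open how arm enters. A reader might also set the attenuated power against the stated 86%. That overstates the cost, since 86% assumes complete data and some power is lost under any imputation.

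What does not stand is that the wording is adequate. The within-arm version appears nowhere in the plan. It is also shown here to be unbiased only under completely random loss, whereas the plan assumes the weaker missing-at-random condition, under which the baseline value may be needed. Nor can the wording be meant for binary outcomes: some questionnaire items are yes/no, but the sentence names VO2peak, and Section 14.3.2 declares all secondary end points continuous.

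**Conclusion.** The point holds in this form: the imputation method is misnamed for continuous end points, and the plan does not settle the one reading under which it would work. The primary A–B estimate may be unbiased, or reduced from 2.5 to about 2.37–2.30 if arm is left out, at a cost of about 3 to 6 power points against 83–84%. The B–C comparison is essentially unaffected.

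These sizes rest on loss at the first site carrying over to the whole trial, on loss that is equal across arms and completely at random, and on the Section 14.2 means and SD. The documents give no losses by arm, so no figure for differential dropout is offered. This should be fixed before analysis; it does not invalidate the design.

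**What to change.** In both Section 14.3.1 and Section 14.3.2, replace logistic regression with normal linear regression or predictive mean matching. State the predictors: arm, the baseline value of the end point, prior chemotherapy and current endocrine therapy. Keep the 20 imputations and Rubin's rule. If a missingness model was intended, the text should say so and state how arm and baseline enter the donor groups.

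Site and sessions attended as further predictors, and a sensitivity run imputing Arms A and B from the Arm C model, are optional and not needed to correct the error.

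The cost is a change of wording and a small change to the analysis program. No new data are needed.
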